3.2.3.8 Fractional exhaled nitric oxide (FeNO)

Airway inflammation will be evaluated using a standardised single-breath FeNO test in accordance with Table 1 and Table 2 of the CSP. A single exhalation technique recommended by the manufacturer will be followed ([Alving et al 2017](#)).

The FeNO test will be performed prior to spirometry.

The NIOX VERO® Airway Inflammation Monitor will be used to measure FeNO. Instructions for use of this monitor will be provided in a separate user's manual.

Change from baseline is obtained as an absolute difference between Week 52 measure and the baseline value as defined in Section 3.1.2 and Section 3.1.3. Changes from baseline at other post-baseline time points will be calculated similarly.

3.2.3.9 Biomarkers

Serum and plasma samples will be collected according to the schedule in Table 2 of the protocol to evaluate the pharmacology of tezepelumab and to evaluate changes in biomarkers related to COPD, inflammation and the thymic stromal lymphopoietin (TSLP) pathway. Baseline and early post-dose levels of serum and plasma biomarkers may also be used to explore for potential predictive biomarkers of response or exposure to tezepelumab. The specific biomarkers that may be analysed are cytokines, chemokines, and inflammatory mediators associated with COPD and the TSLP pathway. The results of exploratory biomarker analyses will not be reported in the CSR but in an addendum, or separately in a scientific report or publication.

The following biomarkers will be collected in this study:

- Total serum immunoglobulin (IgE, IgA, IgG, and IgM)

- Transcriptomic (RNA microarrays, RNA-Seq, and quantitative reverse-transcriptase polymerase chain reaction technologies)
- Nasal epithelial cell and sputum cell transcriptomics (RNA microarrays, RNA-Seq, and quantitative reverse-transcriptase polymerase chain reaction technologies), in a subset of subjects only participating in the sub-study
- Sputum induction and nasal lining fluid (cytokines, chemokines, and inflammatory mediators associated with COPD and the TSLP pathway), in a subset of subjects only participating in the sub-study
- Urine biomarkers

3.2.3.10 Genetic (DNA) sampling

A blood sample for DNA isolation will be collected at one time point only from subjects who have consented to participate in the genetic analysis component of the study.

Samples can be collected at any time after the genetic consent form is signed. The blood sample should be collected at randomisation, however, it may be taken at any visit until the last study visit. In the event of DNA extraction failure, a replacement genetic blood sample may be requested from the subject.

The results of genetic analyses will not be reported in the CSR but in an addendum, or separately in a scientific report or publication.

3.3 Derivation of safety variables

3.3.1 Exposure to IP and treatment compliance

Extent of exposure to IP is defined as the number of days between the date of first dose of IP and the date of last dose of IP inclusive plus the number of days allowance for the dosing interval specified in Section 2.1.5, that is:

Extent of exposure (days) = minimum (date of last dose of IP + 33 days; date of death; date of study withdrawal) - date of first dose of IP + 1

This calculation does not consider any gaps in exposure caused by the subject missing one or more intermediate scheduled 4-weekly doses. Such cases will be identified in the CSR if they occur but will not explicitly be accounted for in any analysis.

The total subject-years exposure for a treatment group will be derived as the sum of the individual subject extents of exposure (days) for that treatment group and divided by 365.25.

Treatment compliance will be calculated as follows:

Treatment compliance (%) = (Total number of actual dosing occasions/total number of expected dosing occasions) x 100%

In order to allow for subjects who discontinue IP early in the compliance calculation, the number of expected dosing occasions will be calculated as the number of scheduled dosing visits up to and including the last available dosing visit for that subject.

3.3.2 Adverse events (AEs) - general

AEs experienced by any subject at any time during the entire study will be coded using the latest version of the Medical Dictionary for Regulatory Activities (MedDRA).

AEs will be separated according to their onset date into the following study periods:

- AEs occurring during screening/run-in period: date of Visit 1 \leq AE onset date $<$ date of first dose of IP
- AEs occurring during on-treatment period: date of first dose of IP \leq AE onset date \leq minimum (date of last dose of IP + 33 days, date of death, date of study withdrawal)
- AEs occurring during post-treatment period (for subjects still being followed up then): date of last dose of IP + 33 days $<$ AE onset date \leq study completion or withdrawal date
- AEs occurring during on-study period: date of first dose of IP \leq AE onset date \leq study completion or withdrawal date

AEs occurring during screening run-in period will be listed only.

If the AE has a completely missing (and unresolvable) onset date, then the AE will be assumed to be treatment-emergent, unless the end date indicates unambiguously that the AE resolved before treatment started. If the AE has a partially missing (and unresolvable) onset date, then the AE will also be assumed to be treatment-emergent, unless either the end date indicates unambiguously that the AE resolved before treatment started, or the partial onset date is in the month/year prior to start of treatment.

For exposure-adjusted summaries of specific AEs, the time at risk for each subject will be derived as the time during the relevant period for analysis during which the subject had no occurrence of that AE. Specifically, for on-treatment AEs, time at risk is defined as:

Time at risk (days) = minimum (date of last dose of IP + 33 days; date of death; date of study withdrawal; date of first adverse event occurrence) – date of first dose of IP + 1

The total time at risk (years) for a treatment group will be derived as the sum of the individual subject's times at risk (days) up to the first adverse event occurrence for that treatment group and divided by 365.25.

In all exposure-adjusted summaries of AEs, multiple occurrences of the same event for a particular subject will not be counted as separate events. A subject will either be considered to have no events of the type being summarised, or one or more occurrences of that event.

3.3.3 Adverse events of special interest

The protocol specifies Adverse Events of Special Interest (AESIs) as those which merit special attention in this trial, and for which derivation details (for those derived from the eCRF), or a statement when the derivation needs to be referenced externally to the SAP (for those derived from MedDRA dictionary terms), are given in Appendix 8.1.

Similar considerations apply to any additional supporting analysis of AESIs, in which MedDRA dictionary-based definitions are used.

3.3.4 Laboratory variables

Clinical chemistry, haematology and urinalysis will be performed by a central laboratory according to the schedule and the variable specifications described in the CSP. Urine samples will be analysed locally and sent for analysis at the central laboratory only if a positive dipstick result for any parameter is observed.

Changes from baseline in continuous laboratory variables will be calculated at relevant visits as specified in Section 3.1.2 and Section 3.1.3.

In all analysis of continuous laboratory variables, any value recorded only as below Lower Limit of Quantification (LLOQ) will be set to LLOQ and included in the analysis. Any value recorded only as above Upper Limit of Quantification (ULOQ) will be set to ULOQ and included in the analysis. Absolute values will be compared to the relevant normal reference range, as provided by the central laboratory, and classified as low (below range), normal (within range or on the limits) or high (above range). All values (absolute and change) falling outside the normal reference ranges will be flagged. These classifications will also be used for shift tables.

For the purposes of shift tables, baseline will be defined as specified in Section 3.1.2. Minimum, maximum and last values calculated across all visits in the relevant study period will use all available values including those from unscheduled and repeat visits, and irrespective of whether the values have been selected for use in summaries using visit windows (see Section 3.1.5).

Urinalysis data will be categorised as negative (0), positive (+), or strongly positive (++, +++, or >+++)
at each time-point.

Liver function tests will also be evaluated as multiples of the upper limit of the normal reference range (ULN). Subjects who meet any of the following criteria at any time during the study will be flagged:

- Aspartate aminotransferase (AST) $\geq 3 \times$ ULN
- Alanine aminotransferase (ALT) $\geq 3 \times$ ULN
- Total bilirubin (TBL) $\geq 2 \times$ ULN

Other multiples of ULN will also be used in the display of liver function tests.

3.3.5 Vital signs

Pre-dose vital signs (pulse rate, systolic blood pressure (BP), diastolic BP (DBP), respiratory rate, body temperature, supplemental O₂ status, oxygen saturation (SpO₂)) will be obtained in accordance with the schedule provided in CSP Table 1 and Table 2.

BMI is calculated as: $BMI = Weight (kg) / [Height (m)]^2$

Changes in vital sign variables between baseline and each scheduled assessment will be calculated at relevant clinic visits as specified in Section 3.1.2 and Section 3.1.3.

Absolute values and changes from baseline (where applicable) will be compared to the relevant reference range tabulated below, and classified as low (below range), normal (within range or on the limits) or high (above range). All values falling outside the reference ranges will be flagged.

Table 3 Vital signs reference ranges				
Parameter	Standard Units	Lower Limit	Upper Limit	Change from Baseline Criteria
Diastolic Blood Pressure (sitting)	mmHg	60	100	±15
Systolic Blood Pressure (sitting)	mmHg	90	160	±30
Pulse Rate (sitting)	Beats/min	50	100	±20
Respiratory Rate	Breaths/min	8	20	
Body Temperature	Celsius	36.0	37.5	
Oxygen Saturation (SpO ₂)	%	90	101	

3.3.6 Twelve lead electrocardiogram (ECGs)

12-lead digital ECG measurements will be recorded in accordance with the protocol, with the baseline visit being defined as any time between Visit 1 and Visit 2 inclusive.

The outcome of the overall evaluation is to be recorded as normal/abnormal in the eCRF, with any abnormalities being recorded as not clinically significant or clinically significant.

3.3.7 Smoking status

Smoking status will be assessed at every visit starting from enrolment (Visit 1) until the end of the last Follow up Visit (Week 64) by collecting the subject's response to a single yes/no question from study personnel: 'What is your smoking status as of today, do you currently smoke? Any change in smoking status between Visit 1 (enrolment) to Visit 3 (randomisation) will result in a screen failure. Smoking status changes during Visit 3 to the end of the last Follow up Visit (Week 64) will be captured on the eCRF but the subject will be permitted to continue in the study.

3.4 Derivation of pharmacokinetic and immunogenicity variables

The third-party vendor analysing the PK samples will be unblinded to the randomised treatment assignments of all subjects; no one from the study team will have access to the PK or ADA data until after the study has been unblinded.

3.4.1 Pharmacokinetic variables

Serum samples will be collected at specified time points according to the schedule of assessment for determination of tezepelumab concentrations. Serum trough tezepelumab concentrations in the tezepelumab group will be summarised by time point.

The assay for determination of tezepelumab concentrations will only be performed using samples for subjects randomised to tezepelumab. Subjects who are randomised to placebo will not have their PK samples analysed by the vendor laboratory.

3.4.2 Immunogenicity variables

Serum samples for determination of tezepelumab concentration and the presence of ADA and neutralizing antibodies (nAb) will be collected at baseline prior to first IP administration, at multiple time point before IP administration during the treatment period, and at selected timepoints in the follow-up period, according to the CSP schedule of assessment.

Samples will be used to determine tezepelumab concentrations, and to measure the presence of ADA and nAb, according to validated assays performed by a designated third-party vendor. Samples that are confirmed positive for ADAs will be further analysed for the presence of nAb.

4. ANALYSIS METHODS

4.1 General principles

4.1.1 Statistical hypotheses for primary efficacy variables

The null hypothesis is that the exacerbation rate on tezepelumab is greater than or equal to the exacerbation rate on placebo. The alternative hypothesis is that the exacerbation rate on tezepelumab is less than the exacerbation rate on placebo, i.e.

$$\begin{aligned} H_0: & \text{Rate ratio (tezepelumab vs Placebo)} \geq 1 \\ H_a: & \text{Rate ratio (tezepelumab vs Placebo)} < 1 \end{aligned}$$

4.1.2 Multiple testing procedure

In this Phase 2a study, in order to describe the nature of the benefits with tezepelumab and to define study success, the primary endpoint will be tested using a one-sided 5% significance level. In addition, and although not powered, the primary endpoint will also be tested using a one-sided 2.5% alpha in order to strongly control type I error. No additional adjustment for multiplicity will be implemented and all additional reported p-values will be considered nominal.

4.2 Analysis methods

4.2.1 Subject disposition, demography, and baseline characteristics

Subject disposition will be summarised using the all subjects analysis set. The number of enrolled subjects and those not randomised (and reason) will be summarised. The number and percentage of subjects within each treatment group will be presented by the following categories; randomised, received IP, did not receive IP (and reason), completed treatment, discontinued treatment (and reason), completed study (subjects who completed IP and study, and subjects who discontinued IP but completed study assessments), and discontinued study (including reason). All randomised subjects will be used as the denominator in percentage calculations for the applicable categories above.

Subject recruitment by country and centre will also be summarised for subjects in the FAS.

Disposition will also be provided for the number and percentage of randomised subjects who consented separately to participate in the optional sub-studies (e.g. DNA sampling, sputum and nasal lining fluid/epithelial cells sub studies).

The number of subjects in each of the analysis sets defined in Section 2.1 will be presented.

The number and percentage of subjects, who discontinued IP, but remained in the study will be presented by treatment group and option of follow up (Section 1.2) at each scheduled timepoint.

Kaplan-Meier plots will be produced summarising separately the time (in days) to premature discontinuation of IP and withdrawal from the study. In both cases, subjects without the premature event will be censored at Week 52.

Demographic data such as age, gender, and race will be summarised by treatment group for subjects in the FAS. All subgroups as defined in Section 3.1.7 will be summarised by treatment group for subjects in the FAS. In addition, the screening blood eosinophil category $\geq 150/\mu\text{L}$ will be further categorised as $\geq 150 - 300/\mu\text{L}$, and $\geq 300/\mu\text{L}$ and summarised by treatment group.

Various baseline characteristics will also be summarised for the FAS by treatment group, which include respiratory disease history, subject characteristics (weight, height and BMI), nicotine use and consumption, baseline lung function (pre- and post-BD FEV₁ (L), FEV₁ (% PN), FVC (L), FVC (% PN), and FEV₁/FVC). The number of historic COPD exacerbations will be plotted.

Stratification factors recorded at randomisation by the IWRS and by eCRF will be summarised by treatment group for the FAS.

Medical and surgical history will be summarised by MedDRA Preferred Term (PT) within the System Organ Class (SOC) level of MedDRA for subjects in the FAS by treatment group. Medical history will be presented separately as current (defined as ongoing at screening) and past (not ongoing at screening).

Important PDs will be summarised by treatment group for subjects in the FAS. COVID-related and non-COVID-related will also be reported separately.

4.2.2 Prior and concomitant medications

The number and percentage of subjects receiving each medication (by ATC classification system codes and generic name) will be presented by treatment group for subjects in the FAS. Separate tables will be presented for allowed and disallowed medications received during each of the following periods as defined in Section 3.1.4: Prior, Concomitant (on-treatment), Concomitant (post-treatment). Disallowed medications will include medications defined as prohibited according to Section 6.5 of the CSP. They will be defined following a physician review (prior to database lock) of the unique combinations of ATC code classifications and generic terms captured.

Tables for baseline maintenance medications (started prior to and ongoing after the first day of IP) will be produced. The number and percentage of patients taking maintenance COPD medications at baseline will be summarised. Summary statistics will be provided for ICS doses, converted to their Fluticasone

Propionate equivalent in micrograms. The number of patients treated with ICS at baseline will be summarised by ATC code and preferred term, with total daily dose (non-converted) at baseline summarised for each preferred term. The total number of days of systemic corticosteroid treatment associated with COPD exacerbations per subject from the first day of IP up to Week 52 will be summarised for the FAS. Prior biologic use for COPD (started prior to V1 and stopped prior to treatment), including those received through a clinical trial where the actual treatment allocation is unknown, will be summarised separately.

Medications will be classified using the latest version of the WHO Drug Dictionary.

Percentages will be calculated relative to the number of subjects in the FAS.

Data from subjects who discontinued IP, regardless of level of follow up chosen will, where possible and relevant, be included in the appropriate medication summaries.

4.2.3 Exposure and compliance

Exposure and treatment compliance derivation details are defined in Section 3.3.1.

Extent of exposure to IP, total duration of study treatment administration (days), total subject-year exposure, compliance, and total number of dosing occasions will be summarised by treatment group, for subjects in the safety analysis set.

4.2.4 Primary outcome variables

4.2.4.1 Primary analyses

The primary efficacy variable is the annual rate of moderate or severe COPD exacerbations up to Week 52 and the primary analysis is to compare the annual COPD exacerbation rate of tezepelumab with placebo. Subjects will be analysed using the full analysis set according to randomised treatment.

The null hypothesis is that the exacerbation rate on tezepelumab is greater than or equal to the exacerbation rate on placebo. The alternative hypothesis is that the exacerbation rate on tezepelumab is less than the exacerbation rate on placebo, i.e.

H_0 : Rate ratio (tezepelumab vs Placebo) ≥ 1

H_a : Rate ratio (tezepelumab vs Placebo) < 1

Annual exacerbation rate in the tezepelumab group will be compared to annual exacerbation rate in the placebo group using a negative binomial model for the primary analysis. The response variable in the model will be the number of COPD exacerbations experienced by a subject during the follow-up for exacerbations. The model will include covariates of treatment group, region, and the number of exacerbations reported at randomization as recorded in IWRS (2, ≥ 3). The logarithm of the subject's

corresponding time at risk will be used as an offset variable in the model to adjust for subjects having different exposure times during which the events occur.

Two separate negative binomial regression models will be generated for the primary analysis for the following estimands:

- **Primary estimand:**
 - **Population** - subjects with moderate to very severe COPD who are randomised and receive at least one dose of IP
 - **Variable** - annual rate of moderate or severe COPD exacerbations up to Week 52
 - **Population-level summary measure** – exacerbation rate ratio of tezepelumab versus placebo
 - **Handling of intercurrent events:**
 - Treatment discontinuation: All available data are used regardless of whether treatment discontinuation occurs;
 - Use of an alternative biologic: All available data are used regardless of whether subject switches to an alternative biologic therapy.

- **Supplemental estimand:**
 - **Population** - subjects with moderate to very severe COPD who are randomised and receive at least one dose of IP
 - **Variable** - annual rate of moderate or severe COPD exacerbations up to Week 52
 - **Population-level summary measure** – exacerbation rate ratio of tezepelumab versus placebo
 - **Handling of intercurrent events:**
 - Treatment discontinuation: All available data are used up until randomised treatment is discontinued;
 - Use of an alternative biologic: All available data are used up until subject switches to an alternative biologic therapy.

The COPD exacerbation rate and the corresponding 90% confidence interval (CI) within each treatment group will be presented. The estimated treatment difference from placebo (i.e. the absolute difference between tezepelumab and placebo, and the rate ratio of tezepelumab versus placebo), corresponding 90% CI, and 1-sided p-value for the ratio will be presented. The 95% CI, and 2-sided p-value for the rate ratio will also be presented. Marginal standardisation methods will be used on the model estimates for all negative binomial analyses, unless otherwise specified.

The negative binomial model under the primary estimand will be repeated for the following, as a supportive analysis to the primary:

- Excluding moderate exacerbations treated with antibiotics alone.

COPD exacerbation summary statistics will be presented based on the full analysis set by treatment group. The individual exacerbation criteria (use of systemic corticosteroids, use of antibiotics, and inpatient hospitalisation or death due to COPD) will also be summarised descriptively. Exacerbations with an alert triggered by ≥ 2 major symptoms, 1 major plus ≥ 1 minor symptom and investigator justified exacerbations will be summarised by severity and treatment group for the FAS. A bar chart showing the percentage of subjects by number of COPD exacerbations over 52 weeks will also be presented.

4.2.4.2 Sensitivity analyses to primary endpoint

Additional sensitivity analyses to assess the robustness of the primary analysis results to missing data are outlined in Appendix 8.2 and to assess the impact of COVID-19 on primary analysis results in Appendix 8.4 .

4.2.4.3 Subgroup analyses for primary endpoint

To explore the uniformity of the detected overall treatment effect on the primary efficacy variable, subgroup analyses and statistical modelling including testing for interaction between treatment and covariates will be performed for subjects in the FAS for all the factors listed in Section 3.1.7.

For each of the subgroup factors, a separate negative binomial regression model will be fitted using the same model terms as used for the primary analysis (described in Section 4.2.4.1), with additional terms for the subgroup main effect and the treatment by subgroup interaction. Region and prior exacerbation count are not included as a covariate if they are the subgroup factor. Imbalanced subgroups which cause convergence issues may be excluded from the analysis.

Similar outputs will be presented for each subgroup as for the primary analysis. The p-value for the interaction term by each treatment group will be presented in the summary tables and forest plots with 95% CI displayed.

It is important to note that the study has not been designed or powered to assess efficacy within any of these pre-defined subgroups, and as such these analyses are considered as exploratory.

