4.2 Scientific Rationale for Study Design

The purpose of this global study is to provide evidence of the efficacy and safety of a 420 mg dose of tezepelumab administered Q4W SC in adults with a history of COPD exacerbations and moderate to very severe COPD receiving triple inhaled maintenance therapy with ICS/LABA/LAMA.

The primary endpoint (COPD exacerbation) is a well-accepted measure for a study in COPD. In order to avoid bias the study will be randomized and double blinded. Subject entry will be stratified by region and prior number of exacerbations (2 vs \geq 3) to ensure equitable distribution for analysis.

Given that TSLP is an upstream and pleiotropic cytokine, the blockade of TSLP is anticipated to have impact on the broad spectrum of inflammatory responses seen in COPD. Subject entry into the study will be monitored to ensure that there are adequate numbers of patients within different phenotypes (level of blood eosinophils and number of exacerbations in the previous year) for analysis.

Induced sputum analysis will be performed in a selected group of sites. The aim of this subset analysis is to further help to answer mechanistic and conceptual questions regarding the effect of tezepelumab in COPD exacerbations. Sputum biomarkers may be measured to evaluate the pharmacology of tezepelumab, exploratory PK, airway microbiome and biomarkers related to COPD, inflammation and the TSLP pathway. Key understandings are believed to come from sputum samples obtained at the time of COPD exacerbation. In these same subjects, analyses of nasal lining fluid and nasal epithelial transcriptomics will be performed to complement the sputum analyses.

4.3 **Justification for Dose**

A 420 mg Q4W dosing regimen was selected for this Phase 2a study in COPD based on the efficacy, safety, and exposure-response relationships found with tezepelumab treatment in patients with severe asthma, as well as safety data from the Phase 1 studies.

Based on the efficacy and safety data, as well as exposure-response analysis, of the Phase 2b asthma study CD-RI-MEDI9929-1146, 210 mg Q4W SC was selected as the optimal dose of tezepelumab for adult and adolescent patients with severe asthma and is confirmed in the Phase 3 studies in severe asthma. Given the uncertainty in the exposure-response relationship in COPD compared to asthma patients, a higher dose of 420 mg Q4W was selected to ensure maximum efficacy in this proof-of-concept study in COPD patients.

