1.2 Study design

This is a Phase 2a, multicenter, randomised, double-blind, placebo-controlled, parallel group study to evaluate the efficacy and safety of tezepelumab 420 mg administered by subcutaneous (SC) injection every 4 weeks (Q4W) in subjects with moderate to very severe COPD receiving triple inhaled maintenance therapy (inhaled corticosteroids (ICS), long-acting beta agonist (LABA) and long-acting muscarinic antagonist (LAMA)), and having had ≥ 2 documented COPD exacerbations in the 12 months prior to Visit 1. Approximately 30% of subjects will have had at least 1 severe exacerbation (an exacerbation resulting in hospitalisation) within the 12 months prior to Visit 1. Approximately 40% of subjects will have had ≥ 3 exacerbations within the 12 months prior to Visit 1.

The study will consist of a screening period for approximately 6 weeks, a treatment period of 52 weeks and a post-treatment follow-up period of 12 weeks. Subjects will be randomised in a 1:1 ratio to either 420 mg of tezepelumab or matching placebo both administered Q4W SC. During the treatment period, investigational product (IP) will be administered from Day 1 until Week 48. No IP will be administered at Week 52. Subjects that complete the 52-week study visit will complete a 12 week off-treatment follow-up period for assessments. Subjects who discontinue IP during the study will be encouraged to undergo appropriate study visits/procedures for the full 52-week period.

The study will randomise approximately 338 subjects 1:1 to either tezepelumab or placebo, stratified by region, and number of prior exacerbations recorded at randomisation in IWRS. Approximately 20% of the subjects will be targeted to have ≥ 300 eosinophils/ μL , approximately 40% of the subjects between ≥ 150 to < 300 eosinophils/ μL and a maximum of approximately 40% of the subjects with < 150 eosinophils/ μL at enrolment. When the target percentage of subjects for the prior exacerbations or eosinophil subgroup in a region or overall is reached, consideration will be given to closing the Interactive Web Response System (IWRS) randomisation for that subgroup [by region or overall]. Once a subgroup is closed, subjects in the screening period in the closed subgroup will not be allowed to be randomised and will be screen failed.

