The sample size has been reassessed due to the potential for reduced exacerbation rates due to limited person-to-person contact and exposure to respiratory infections during the COVID-19 pandemic. Assuming the same treatment effect (0.7) and dispersion parameter (0.6) as originally assumed, a sample size of 169 subjects per treatment arm (338 overall) will maintain the study power if the placebo exacerbation rate is as low as 1.2 exacerbations/subject-year.

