3.1.7 Definition of subgroups

The following subgroups are defined for the purpose of primary efficacy subgroup analysis and for secondary efficacy subgroup analysis (SGRQ and pre-BD FEV₁ only):

- Screening blood eosinophils group: <150/μL, ≥150/μL
- Baseline blood eosinophils group: <150/μL, ≥150 to <300/μL, ≥300/μL
- Baseline clinic visit FeNO group 1: <25ppb, ≥25ppb
- Baseline clinic visit FeNO group 2: <25ppb, ≥25 to <50ppb, ≥50ppb
- Age category at study entry: ≥40 to <65 years, ≥65 to <80 years
- Gender: Male, Female
- Race: White, Black or African American, Asian, Other
- Baseline Body Mass Index (BMI): <25 kg/m², ≥25 to 30 kg/m², ≥30 kg/m²
- Chronic bronchitis at baseline (presence or absence of chronic bronchitis as recorded in RESHISTE module of the eCRF)
- Emphysema at baseline (presence or absence of emphysema as recorded in RESHISTE module of the eCRF)
- COPD characteristics at baseline (No emphysema or chronic bronchitis, Only emphysema, Only chronic bronchitis, Emphysema and chronic bronchitis as recorded in RESHISTE module of the eCRF)
- Prior severe exacerbation at randomization as recorded in eCRF: Yes, No
- Prior exacerbation counts recorded at randomisation as recorded in IWRS: 2, ≥3
- Baseline smoking status: Current, Former
- Baseline smoking status: ≥baseline median number of pack years, <baseline median number of pack years

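### Within this SAP, effect modification by blood eosinophils (and FeNO) is tested only on cut groups; if the effect is log-linear in the eosinophil count, this costs about 5 to 20 points of power against a continuous log-count interaction.

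*SAP*

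**What the plan says.** SAP 4.2.4.3 fits one negative binomial model per subgroup factor. It takes the primary model terms and adds the subgroup main effect and the treatment-by-subgroup interaction; "testing for interaction between treatment and covariates will be performed for subjects in the FAS for all the factors listed in Section 3.1.7". SAP 3.1.7 gives two eosinophil factors: "Screening blood eosinophils group: <150/μL, ≥150/μL" and "Baseline blood eosinophils group: <150/μL, ≥150 to <300/μL, ≥300/μL". FeNO also enters twice, cut at 25 ppb and at 25 and 50 ppb. The interaction p-values are reported, but no significance level is set for them. The same section says the study was not designed or powered for subgroups and calls these analyses exploratory. SAP 4.1.2 makes all p-values beyond the primary tests nominal.

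Eosinophil level is also a recruitment variable. Protocol 4.2 states: "Subject entry into the study will be monitored to ensure that there are adequate numbers of patients within different phenotypes", naming eosinophil level as one of the phenotypes. Protocol 4.1 and SAP 1.2 set target shares for the three bands and allow a band to be closed to randomisation once its target is reached.

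Protocol 9.5.3 leaves interaction testing to the SAP. Protocol 9.5.6 and SAP 4.2.6.2 refer other biomarker work to separate plans, which are not among the documents.

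**The concern.** The design spends recruitment effort, including possible screen failures from closed bands, to obtain a spread of eosinophil counts. The test of whether the effect varies with the count then treats everyone within a band as identical. If the effect changes steadily with the count, that discards information already collected, and a real gradient is more likely to be missed than it needs to be. At stake is an exploratory answer about phenotype, not the primary result.

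**Working it through.** **Inputs.** From SAP 1.3: "a sample size of 169 subjects per treatment arm (338 overall) will maintain the study power" at a placebo rate of 1.2 per year, rate ratio 0.70, dispersion k = 0.6. Uniform drop-out of 10% gives a mean exposure of t = 0.95 year. From SAP 1.2: "Approximately 20% of the subjects will be targeted to have" at least 300 eosinophils/µL, and "a maximum of approximately 40% of the subjects with" fewer than 150. Three inputs are assumptions the documents do not supply: a log-normal count through those two shares, the size and shape of the gradient, and a two-sided 5% test level.

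**Step 1: reproduce the plan's figure.** n per arm = (z_α + z_β)² × [1/(r₀t) + k + 1/(0.7·r₀t) + k] / (ln 0.7)². With r₀ = 1.6 and one-sided 5%: 6.183 × (0.658 + 0.940 + 1.2) / 0.1272 = 136, as stated. Power at 141 per arm is 81.3% (stated 81.2%). For the updated design, SE(log rate ratio) = √[(0.877 + 1.253 + 1.2)/169] = 0.140, and one-sided 5% power is 81.5% before any futility loss.

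**Step 2: the count.** SD of the log count = ln 2 / (z₀.₈₀ − z₀.₄₀) = 0.693/1.095 = 0.633. Median = 150 × exp(0.633 × 0.253) = 176.

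**Step 3: information kept by the cuts.** Two groups: φ(0.253)²/(0.4 × 0.6) = 0.386²/0.24 = 62%. Three groups, with standardised means −0.966, 0.266 and 1.400: 0.4 × 0.933 + 0.4 × 0.071 + 0.2 × 1.960 = 79%, spread over 2 degrees of freedom.

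**Step 4: power under a log-linear effect.** The rate ratio is 0.70 at the median and is multiplied by q per doubling of the count. The slope per SD is (ln q/ln 2) × 0.633, and the noncentrality is (slope/0.140)². This is multiplied by 0.62 or 0.79 for the grouped tests. For q = 0.70 the slope is −0.326 and the noncentrality 5.38 (continuous), 3.35 (two groups, 1 df) and 4.27 (three groups, 2 df).

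| q per doubling | Approx. group rate ratios | Continuous | Two groups | Three groups | Loss (points) |
|---|---|---|---|---|---|
| 0.90 | 0.77/0.68/0.61 | 10.5% | 8.4% | 7.9% | 2.1, 2.6 |
| 0.85 | 0.81/0.67/0.57 | 18.5% | 13.3% | 12.3% | 5.2, 6.2 |
| 0.80 | 0.85/0.66/0.53 | 30.6% | 20.8% | 19.4% | 9.8, 11.2 |
| 0.75 | 0.90/0.65/0.48 | 46.5% | 31.4% | 30.0% | 15.0, 16.5 |
| 0.70 | 0.96/0.64/0.44 | 64.1% | 44.8% | 44.0% | 19.2, 20.1 |
| 0.65 | 1.02/0.63/0.40 | 80.0% | 59.9% | 60.1% | 20.1, 19.9 |

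Simulation agrees: 2,800 trials per slope, negative binomial likelihood-ratio tests, without the region and prior-exacerbation covariates. For q from 0.85 to 0.65 the simulated losses run from 5.4 and 6.7 points to 18.5 and 19.3. At q = 0.50, where every test is near full power, the analytic loss falls to about 5 and 4 points.

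**Step 5: other shapes.** Same inputs, power for continuous / two groups / three groups:

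- Step at 150 (rate ratio 1.0 below, 0.55 above): 40 / 56 / 46%.
- Step at 300 (0.80 below, 0.40 above): 19 / 9 / 34%.
- Decline between 100 and 200, then flat (group rate ratios about 0.91/0.58/0.55): 35 / 38 / 30%.

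**The case against.** The strongest reply is that the loss follows from the assumed shape. Step 4 generates the effect from the same log-linear form that the continuous model fits, and the documents give no dose-response shape. Step 5 bears this out. A step at either cut favours one of the planned tests, and a smooth effect that flattens above about 200 leaves the continuous model with no advantage over two groups. This stands, and it limits the claim to log-linear effects.

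It is also fair that the cuts match the recruitment bands, so grouped estimates have a clear rationale, and that capping and closing bands makes the log-normal an approximation. The two-group factor uses the screening count and the three-group factor the baseline count; the calculation treats them as one value. No distribution is given for FeNO, so no loss is calculated there.

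The reply that the analysis is exploratory and unpowered stands as to importance: no decision rule in the documents uses this p-value. It does not remove the case for a cheap addition, because keeping 62% or 79% of the information matters more when power is already low.

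**Conclusion.** The point holds as an optional improvement. Within this SAP, effect modification by eosinophils and FeNO is tested only on cut groups. For a log-linear eosinophil effect with multipliers of 0.85 to 0.65 per doubling, and under the stated assumptions, the grouped tests give up about 5 to 20 points of power. They give up 2 to 3 points for a weak gradient.

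Three stronger readings are tempting and are not supported:

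- A reader might infer that cut groups lose power for any graded effect. The plateau case shows otherwise, and steps at the cuts reverse the order.
- A reader might infer that the continuous test should replace the grouped ones. That would give up 16 points against the two-group test for the step at 150 (56% against 40%), and 15 points against the three-group test for the step at 300 (34% against 19%).
- A reader might infer that the next study's population will be chosen on this p-value. Protocol 9.5 says results at the primary lock will inform Phase 3 design, but nothing ties population choice to this test.

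Nor can it be said that no continuous analysis is planned anywhere, since the separate biomarker plans are not available. The primary test is untouched.

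**What to change.** In SAP 4.2.4.3, keep the grouped interaction tests and forest plots as they are. Add one prespecified model each for blood eosinophils and FeNO: the primary negative binomial model plus log2(baseline value) and treatment × log2(baseline value). State a rule for zero counts, for example a small fixed offset, because the logarithm is undefined there. Report the nominal interaction p-value beside the grouped ones. For eosinophils, also give the model rate ratios at, for example, 100, 150 and 300 cells/µL. To count as prespecified, the wording must be in place before the primary database lock.

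The cost is SAP text and one more model per biomarker on data already collected. The downsides are a log-linearity assumption and one more nominal p-value per biomarker; the retained grouped results keep a step or plateau visible.
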